3.8 Early Withdrawal (EW)

If a randomized subject is withdrawn from the study prior to completion, the subject will be instructed to return to the clinic the next day and the Visit 9 procedures will be performed. In addition, subjects will perform the DTSQs and DTSQc questionnaires. Subjects will then be discharged from the study.

Any subject with a possible study treatment related AE at the time of EW will be followed until resolution or stabilization of the event.

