3.5.4 Visit 9 (Part 2 Week 10 ± 7 days)

Subjects will report to the clinic in the morning following a 10-hour fast and the following procedures will be performed:

- Review of prior and current medications and supplements.
- Physical examination.
- 12-lead ECG.
- Measurement of weight.
- Measurement of vital signs (SBP/DPB and heart rate).
- Remove CGM device and download the data.
- Collect and review the paper diary for completeness of entries.
- Collection of fasted blood and urine samples for:
 - o Clinical safety labs, including hematology, serum chemistry (with FPG, A1C, and immunogenicity testing), and urinalysis (see Section 6.1.5 for list of tests).
 - o Urine pregnancy test (WCBP only).
- Perform MMTT test (Section 6.2.1).
 - o Administer double-blind Study medication dose (32 mg or placebo) if subject is in the BID or TID arm 45 minutes prior to MMTT test.
 - Collection of blood samples for insulin, glucose, and C-peptide analysis prior to the start of the MMTT test at -50 and -5 minutes.
 - O Additional blood samples will be drawn at 60and 120 minutes (± 10 minutes) post-prandially to obtain insulin and glucose levels.
 - O Blood samples for C-peptide will also be drawn at 60 minutes (± 10 minutes).
- Review e-diary for completeness of entries, SMBG data and hypoglycemic events. Collect e-diary.
- Collect unused medication and review e-diary for compliance.
- Record adverse events.
- Remind subjects to arrive fasting for follow-up Visit 10.

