- ⁵ At Visit 3 subjects will undergo a 2-hour MMTT. A final MMTT will occur on the final study visit also 45 min after administration of double-blind study medication.
- ⁶At each visit as indicated, subjects will be reminded about insulin dosing instructions and symptoms of potential hypoglycemia.
- ⁷Review FPG data from both in-clinic measurements and SMBG measurements and A1C to determine if a subject qualifies for rescue therapy based on Investigator discretion and the criteria outlined in Section 3.7. Subjects eligible for rescue should undergo a Rescue Visit (Section 3.7).

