4.3 Subject and Trial Discontinuation

Subjects may choose to withdraw from this study at any time for any reason without penalty of jeopardizing their health care or loss of benefits to which the subject is otherwise entitled.

Within the provisions of informed consent and good clinical judgment with respect to safety, every attempt will be made to have subjects complete the study. Reasons for subject discontinuation include, but are not limited to the following:

- 1. Subject experiences an AE that in the judgement of the Investigator poses a significant risk to the subject for continued participation in the study.
- 2. Subject uses a prohibited medication (listed in Section 5.7) that in the judgment of the Investigator poses a significant risk to the subject for continued participation in the study or that will interfere with the interpretation of the results of the study.
- 3. Subject becomes pregnant.
- 4. Significant protocol violation or noncompliance on the part of the subject or the Investigator.
- 5. Intercurrent illness that requires treatment that is not consistent with the protocol requirements, or intercurrent illness or the associated treatment that in the judgment of the Investigator poses a significant risk to the subject for continued participation in the study.
- 6. Episodes of hypoglycemia not responsive to changes in diet or dose regimen (Section 7.3.1)
- 7. Subject meets one of the exclusion criteria during the study
- 8. Subject wishes to withdraw for any reason.
- 9. Sponsor elects to end the study, or the Investigational Site elects to end the study at their site.
- 10. Any other reason that in the judgment of the Investigator poses unacceptable risk to the subject.

Subjects who withdraw from the study prior to treatment may be replaced. Subjects who are withdrawn and have received at least one treatment will not be replaced.

Except in cases of emergency, the Investigator should consult with the Sponsor and the Medical Monitor before removing the subject from the study. In some circumstances, it may be necessary to temporarily interrupt treatment as a result of AEs that may have an unclear relationship to study treatment. The investigator should obtain approval from the Sponsor and Medical Monitor before restarting study treatments that were temporarily discontinued for an AE.

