In the event that a subject discontinues the study prior to completion, the date the subject is withdrawn and the reason for discontinuation will be recorded in the source documents and eCRF. Although a subject will not be obliged to give his/her reason for withdrawing prematurely, the investigator will make a reasonable effort to obtain the reason while fully respecting the subject's rights.

All subjects who are randomized and treated (i.e., received any amount of study treatment) will be included in the safety analyses. Thus, every effort will be made to contact any subject who fails to attend any follow-up appointments/contacts, in order to ensure that he/she is in satisfactory health. If a subject withdraws from the study as a result of meeting discontinuation criteria (Section 4.3) after the start of study treatment administration, reasonable efforts should be made to have the subject return for the early withdrawal evaluations (Section 3.8). Any subject withdrawn due to a

suspected study treatment -related AE should be followed until resolution or stabilization of the event.

If a subject becomes pregnant, study treatment will be discontinued immediately. The subject will be followed until delivery or other termination of pregnancy for outcome.

The Sponsor has the right to terminate this study, and the Investigator/Investigational Site has the right to close the site, at any time, although this should occur only after consultation between involved parties. The Investigator will notify the IRB in writing of a premature termination of a study or closure of Investigational Site, and will send a copy of the notification to the Sponsor.

Events that may trigger premature termination of a study or closure of an Investigational Site include, but are not limited to, a new toxicity finding, a request to discontinue the trial from a regulatory authority, non-compliance with the protocol, GCP violations, slow recruitment/low enrollment, or change in development plans for the study treatment.

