6.2 Efficacy Assessments

6.2.1 Mixed Meal Tolerance Test (MMTT)

All subjects will have mixed meal tolerance testing throughout the study. MMTT will be performed as indicated in Table 1. All subjects will report to the research center following a 10 hour fast prior to taking morning medications. All MMTT should be scheduled at the same time for each subject. If the fasting blood glucose value measured on the day of the Rescue Visit remains > 250 mg/dL, then no MMTT test will be performed but an attempt will be made to reschedule.

- 1) Baseline blood samples will be drawn at -50 minutes (±10 minutes) and at -5 minutes (±5 minutes) from the start of the meal. Blood samples will be drawn for insulin, glucose, and C-peptide levels.
- 2) 45 minutes prior to the start of the meal (time 0), subjects will receive their morning dose of study drug (active or placebo, depending on the Visit). Subjects' blood glucose (BG) must be >70 mg/dL and <250 mg/dL prior to initiating dosing.
- 3) At 0 time, the subject will receive a standardized meal, which should be ingested over 5 minutes.
- 4) Additional blood samples will be drawn at 60 and 120 minutes (\pm 10 minutes) after the start of the meal to obtain insulin and glucose levels. Samples for C-peptide will also be drawn at 60 minutes (\pm 10 minutes).

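### Early Withdrawal imports all Visit 9 procedures, including a study drug dose in BID and TID arms; this contradicts Section 4.3 for pregnancy and sits badly with it for safety withdrawals

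*Combined protocol and SAP*

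**What the plan says.** Section 3.8 defines the Early Withdrawal visit by cross-reference: "the subject will be instructed to return to the clinic the next day and the Visit 9 procedures will be performed". It adds two questionnaires and removes nothing. Section 4.3 sends subjects who meet a discontinuation criterion after starting treatment to this visit.

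The Visit 9 list in Section 3.5.4 contains an MMTT with the instruction "Administer double-blind Study medication dose (32 mg or placebo) if subject is in the BID or TID arm 45 minutes prior to MMTT test". Section 6.2.1, the general MMTT procedure, gives the dose with no regimen limit: "45 minutes prior to the start of the meal (time 0), subjects will receive their morning dose of study drug". Table 1 footnote 5 does the same: "A final MMTT will occur on the final study visit also 45 min after administration of double-blind study medication". The one condition on the dose is in Section 6.2.1: "Subjects' blood glucose (BG) must be >70 mg/dL and <250 mg/dL prior to initiating dosing".

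Section 4.3 lists among the reasons for discontinuation an adverse event (AE) that poses significant risk, hypoglycemia that does not respond to diet or dose changes, and pregnancy. On treatment itself it makes two statements. For pregnancy: "If a subject becomes pregnant, study treatment will be discontinued immediately". For temporary holds: "The investigator should obtain approval from the Sponsor and Medical Monitor before restarting study treatments that were temporarily discontinued for an AE".

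**The concern.** The visit for subjects who have just been taken off the study borrows the procedures of the visit for subjects who completed treatment. One of those procedures is a further dose of study drug. Followed to the letter, a site gives a BID or TID subject blinded study drug the day after the decision to withdraw, whatever the reason for it.

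A pregnant subject is the clearest case, because the protocol elsewhere orders treatment to stop at once. Section 7.6.1 states that the potential for fetal harm is not known. Visit 9 includes a urine pregnancy test, but no text links a positive result to withholding the dose. The site cannot comply with both sections: withholding departs from Section 3.8, and dosing departs from Section 4.3.

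At stake is avoidable exposure in the subjects for whom the protocol is most concerned to limit it, and inconsistent conduct between sites that resolve the conflict differently.

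**Working it through.** The plan states no figure on this point, so the check is a comparison of texts followed by a count of who could be affected.

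**Does Section 3.8 reach the dose?**
- Section 4.3 directs discontinued subjects to the Section 3.8 evaluations.
- Section 3.8 imports the Visit 9 procedures without exception.
- Section 3.5.4 includes the pre-MMTT dose for BID and TID arms.
- So the dose is part of the visit for those arms. QHS arms are reached only if Section 6.2.1 and footnote 5 override the visit-specific limit in Section 3.5.4, and the documents do not say which prevails. That is an inconsistency in its own right.
- The 20 non-randomized TID subjects fall outside the literal wording of Section 3.8, which speaks of randomized subjects.

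**Does the dose conflict with Section 4.3, reason by reason?**
- Pregnancy: an express immediate stop against a scheduled dose. Direct contradiction in BID and TID arms.
- Risk-posing AE: Section 4.3 has no express stop rule for withdrawn subjects. It requires Sponsor and Medical Monitor approval to restart after a temporary hold, while Section 3.8 schedules a dose after withdrawal with no approval step. Conflict by implication.
- Non-responsive hypoglycemia: a listed reason for discontinuation with no separate rule on dosing afterwards. Conflict by implication.

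**Does the glucose condition resolve it?** No. A value above 70 and below 250 mg/dL permits the dose in a pregnant subject, or in one withdrawn for an AE or for hypoglycemia on earlier days.

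**How many subjects are in arms with the dose?** Inputs: Cohort A has 265 randomized 1:1:1 to QHS, BID and TID, with placebo to active 1:3 within each (Section 5.2). Cohort B has 75 in five groups of 15, two of them BID and both active (Sections 5.2 and 8.2.2).
- Cohort A BID and TID: 265 × 2/3 = 176.7
- Cohort B BID: 2 × 15 = 30
- Total: 206.7 of 265 + 75 = 340, or 61%. The remaining 39% are in QHS arms.
- On active drug: 176.7 × 3/4 + 30 = 132.5 + 30 = 162.5

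**How many might withdraw early?** The dropout allowance is about 20%. It reproduces the plan's completers: 240 × 0.8 = 192 in Cohort A (Section 8.2.1) and 75 × 0.8 = 60 in Cohort B (Section 8.2.2).
- All BID and TID: 0.20 × 206.7 = 41.3
- Active BID and TID: 0.20 × 162.5 = 32.5

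**How many for safety reasons?** The documents give no share. Assuming 10% to 30%: 0.10 × 32.5 = 3.3 to 0.30 × 32.5 = 9.8.

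Using the 240 of Section 8.2.1 instead of 265 gives 240 × 2/3 × 3/4 + 30 = 150 active, 30 withdrawals, and 3 to 9 for safety reasons. The picture does not change.

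**The case against.** The strongest reply is that no site would read Section 3.8 as an order to re-dose. Where Section 6 extends an assessment to Early Withdrawal it says so: physical examination (6.1.3), ECG (6.1.4) and antibody testing (6.1.5.3). The MMTT section does not. It refers to Table 1, which marks the MMTT at Visits 3 and 9 and at the Rescue Visit only. It also speaks of the subject's morning dose, which presumes an ongoing regimen. Section 4.3 operates within good clinical judgment on safety, and most investigators would withhold the dose.

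This has weight as evidence of intent. It does not change Section 3.8, which defines the visit, imports the whole list and makes no exception. A protocol should not rely on sites departing from it.

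Other parts of the reply stand and limit the point. A reader might infer that Section 4.3 forbids the dose equally for all three reasons. It does so expressly for pregnancy alone, and the restart rule concerns temporary holds. A reader might infer that every withdrawn subject is re-dosed, but Section 3.5.4 confines the dose to BID and TID arms. A reader might also infer that subjects are dosed, discharged and lost to view. In fact Section 3.8 follows a possible treatment-related AE present at that visit to resolution or stabilization, Section 4.3 does the same for withdrawals due to a suspected related AE, and Section 7.5 follows serious events up to 30 days after the last dose. Finally, one might argue that the extra dose would confuse causality assessment under Section 7.6. Nothing in the documents shows this, and recurrence on re-exposure is itself one of the alternatives that supports the highest causality category.

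**Conclusion.** The plan is wrong as written. In BID and TID arms, about 207 of 340 randomized subjects, Section 3.8 schedules a study drug dose at Early Withdrawal with no exception by reason. For pregnancy this contradicts an explicit rule in Section 4.3. For risk-posing AEs and non-responsive hypoglycemia the conflict is implied and the matter is left unaddressed. The regimen limit in Section 3.5.4 and its absence in Section 6.2.1 and footnote 5 are a further inconsistency.

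The contradiction rests on the text and needs no count. The counts are upper bounds: at most about 32 early withdrawals on active drug in these arms, and at most about 3 to 10 of them for safety reasons. They assume that dropout is 20% in every arm, that the safety share is 10% to 30% (not from the documents), and that every such subject attends, meets the glucose condition and completes the MMTT. Section 4.3 promises only reasonable efforts to bring subjects back, so these figures should not be read as the number who would be dosed. The number of pregnancies cannot be estimated from the documents.

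**What to change.** In Section 3.8, replace the reference to Visit 9 with an explicit list of Early Withdrawal procedures. State there, by reason for withdrawal (AE, hypoglycemia, pregnancy, other), whether the pre-MMTT dose applies and whether the MMTT applies. Mirror this in an Early Withdrawal column in Table 1. Bring Sections 3.5.4 and 6.2.1 and Table 1 footnote 5 into line with each other on which regimens the dose concerns, and all of them into line with Section 4.3. Which rule is clinically right is for the sponsor's clinical team.

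If some subjects are to have the MMTT without the dose, the analysis plan should say whether those results are used, since they would not be measured under Visit 9 conditions.

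The cost is protocol wording, one table column and possibly some early-withdrawal MMTT data. The HbA1C sample at that visit is a separate fasted draw and does not depend on the dose or the MMTT.

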3.9 Schedule of Events

Table 1 below describes the daily schedule of events from Screening through Follow-Up Visit 10.

Table 1. Daily Schedule of Events from Screening through Follow-Up Visit

		Rur	ı-In	Par	t 1	Part 2			Rescue	Follow- Up		
Visit	Screen	1	2	3	4	5	6	7	8	9	RV	10
Week	-3 to -1	0	1	0	1	0	1	4	8	10	Variable	12
Informed Consent	X											
Inclusion/Exclusion	X	X		X								
Medical History/Disease History Questionnaire	X											
Concomitant Medications	X	X	X	X	X	X	X	X	X	X	X	X
Physical Examination	X			X						X	X	X
12-lead ECG	X									X	X	
Height and Weight ¹	X	X		X		X			X	X	X	X
Vital Signs ²	X	X	X	X	X	X	X	X	X	X	X	X
Chemistry, Hematology, Urinalysis	X	X		X		X			X	X	X	X
Urine Drug Screen	X			X		X						
Pregnancy Test ³	X	X	X	X	X	X	X	X	X	X	X	X
C-peptide and TSH	X											
Fasting Blood Glucose	X	X	X	X	X	X	X	X	X	X	X	X
HbA1C	X	X		X		X			X	X	X	X
Immunogenicity Testing	X									X	X	X
Randomization ⁴				X								
CGM On/Off (Dispense/Review paper diary)		On		Off					On	Off		

		Rui	n-In	Par	t 1			Part	2		Rescue	Follow- Up
Visit	Screen	1	2	3	4	5	6	7	8	9	RV	10
Week	-3 to -1	0	1	0	1	0	1	4	8	10	Variable	12
Mixed Meal Tolerance Test ⁵				X						X	X	
Dispense e-diary and Train on Use		X										
SMBG/Nutrition/Hypoglycem ia Symptom Training		X		X		X						
Review e-diary SMBG data			X	X	X	X	X	X	X	X	X	
Review e-diary and assess for hypoglycemic events			X	X	X	X	X	X	X	X	X	
Collect study medication and review e-diary for compliance			X	X	X	X	X	X	X	X	X	
Dispense SB placebo		X	X									
Dispense study medication (active or placebo)				X	X	X		X	X			
Subject Training/Insulin Dosing Review ⁶				X	X	X	X	X	X	X	X	
Assess for Rescue or Termination ⁷						X	X	X	X		X	
Collect e-diary										X		
DTSQs		X				X			X		X	
DTSQc									X		X	
Adverse Events		X	X	X	X	X	X	X	X	X	X	X

Table 1 Footnotes

- ¹Height will be measured at Screening only. Weight will be measured as indicated.
- ²Heart rate and blood pressure.
- ³Serum pregnancy test at Screening, urine pregnancy test at Visits 1-10 and at Rescue Visits.
- ⁴ Randomization will occur at Visit 3. Subjects will be dispensed single-blind placebo to be taken QHS during the runin period. At Visit 3, subjects will be dispensed ORMD-0801 or placebo to be administered according to their randomization schedule. For Cohort A, subjects randomized to ORMD-0801 will start their dose at 16 mg at Visit 3, increase to 24 mg at Visit 4, and increase to 32 mg at Visit 5.
- ⁵ At Visit 3 subjects will undergo a 2-hour MMTT. A final MMTT will occur on the final study visit also 45 min after administration of double-blind study medication.
- ⁶At each visit as indicated, subjects will be reminded about insulin dosing instructions and symptoms of potential hypoglycemia.
- ⁷Review FPG data from both in-clinic measurements and SMBG measurements and A1C to determine if a subject qualifies for rescue therapy based on Investigator discretion and the criteria outlined in Section 3.7. Subjects eligible for rescue should undergo a Rescue Visit (Section 3.7).

4 STUDY SUBJECT SELECTION

4.1 Inclusion Criteria

Each subject must meet all of the following criteria to be eligible for the study:

- 1. Male and female subjects aged 18 and older.
- 2. Established diagnosis of T2DM for at least 6 months prior to Screening, with an HbA1C ≥ 7.5%.
- 3. Stable dose of metformin (at least 1500 mg or maximal tolerated dose)/oral antidiabetic (OAD) for a period of at least 3 months prior to Screening.
- 4. Taking metformin only or metformin in addition to no more than two of the following: SU, DPP-4, SGLT-2, or TZD.
- 5. Body mass index (BMI) of up to 40 kg/m² at Screening and stable weight, with no more than 5 kg gain or loss in the 3 months prior to Screening.
- 6. Renal function eGFR $> 30 \text{ ml/min/}1.73 \text{ m}^2$
- 7. Females of childbearing potential must have a negative serum pregnancy test result at Screening.
- 8. Females who are not of childbearing potential are defined as:
 - a. post-menopausal (defined as at least 12 months with no menses in women ≥45 years of age) or
 - b. has had a hysterectomy and/or bilateral oophorectomy, or had bilateral tubal ligation or occlusion at least 6 weeks prior to Screening
- 9. Subjects who are of childbearing potential must:
 - a. agree to remain abstinent from heterosexual activity[†] or agree to use (or have their partner use) acceptable contraception to prevent pregnancy within the projected duration of the trial and for 14 days after the last dose of blinded investigational product. Two methods of contraception will be used to avoid pregnancy. Acceptable combinations of methods include:
 - i. Use of one of the following double-barrier methods: diaphragm with spermicide and a condom; cervical cap and a condom; or a contraceptive sponge and condom
 - ii. Use of hormonal contraception (any registered and marketed contraceptive agent that contains an estrogen and/or a progestational agent [including oral, subcutaneous, intrauterine and intramuscular agents, and cutaneous patch]) with one of the following: diaphragm with spermicide; cervical cap; contraceptive sponge; condom; vasectomy; or IUD.
 - iii. Use of an IUD with one of the following: condom; diaphragm with spermicide; contraceptive sponge; vasectomy; or hormonal contraception (see above).
 - iv. Vasectomy with one of the following: diaphragm with spermicide; cervical cap; contraceptive sponge; condom; IUD; or hormonal contraception (see above).

[†] Abstinence can be used as the sole method of contraception if it is in line with the subject's preferred and usual lifestyle and if considered acceptable by local regulatory agencies and

ethics committees. Periodic abstinence (e.g., calendar, ovulation, sympto-thermal, postovulation methods, etc.) and withdrawal are not acceptable methods of contraception.

Page 35

4.2 Exclusion Criteria

Subjects who meet any of the following criteria must be excluded from the study:

- 1. Subjects with insulin-dependent diabetes
 - a. has a history of type 1 diabetes mellitus or a history of ketoacidosis, or subject is assessed by the investigator as possibly having type 1 diabetes mellitus confirmed by a C-peptide <0.7 ng/mL (0.23 nmol/L).
 - **b.** has a history of other specific types of diabetes (e.g., genetic syndromes, secondary pancreatic diabetes, diabetes due to endocrinopathies, drug- or chemical-induced, and post-organ transplant).
- 2. Treatment with glucosidase inhibitor, insulin secretagogues (other than sulfonylureas), glucagon-like peptide 1 (GLP-1) agonists within 3 months prior to Visit 1.
- 3. History of any basal, pre-mix or prandial insulin (greater than 7 days) within 6 months prior to Screening.
- 4. History of >2 episodes of severe hypoglycemia within 6 months prior to Screening.
- 5. History of hypoglycemic unawareness (episodes of severe hypoglycemia with seizure or requiring third party intervention or documented low blood glucose without associated autonomic symptoms)
- 6. Subjects with the following secondary complications of diabetes:
 - a. Active proliferative retinopathy as confirmed by a dilated ophthalmoscopy/retinal photography examination performed (by a qualified person as per the country legislation) within 6 months prior to Screening.
 - b. Renal dysfunction: eGFR < 30 ml/min/1.73 m²
 - c. History of proliferative retinopathy or severe form of neuropathy or cardiac autonomic neuropathy (CAN)
 - d. Uncontrolled or untreated severe hypertension defined as systolic blood pressure above or equal to 180 mmHg and/or diastolic blood pressure above or equal to 120 mmHg
 - e. Presence of unstable angina or myocardial infarction within 6 months prior to Screening, Grade 3 or 4 congestive heart failure (CHF) according to the New York Heart Association (NYHA) criteria, valvular heart disease, cardiac arrhythmia requiring treatment (other than treated atrial fibrillation), pulmonary hypertension, cardiac surgery, history/occurrence of coronary angioplasty and/or stroke or transient ischemic attack (TIA) within 6 months prior to Screening.
- 7. Subjects with psychiatric disorders which, per investigator judgment, may have impact on the safety of the subject or interfere with subject's participation or compliance in the study.
- 8. Subjects who needed (in the last 12 months) or may require systemic (oral, intravenous, intramuscular) glucocorticoid therapy for more than 2 weeks during the study period.
- 9. Laboratory abnormalities at Screening including:
 - a. C-peptide < 0.7 ng/mL

- b. Abnormal serum thyrotropin (TSH) levels below the lower limit of normal or >1.5X the upper limit of normal
- c. Elevated liver enzymes (alanine transaminase (ALT), alanine aminotransferase (AST), alkaline phosphatase) >2X the upper limit of normal.
- d. Very high triglyceride levels (>600 mg/dL); a single repeat test is allowable.
- e. Any relevant abnormality that would interfere with the efficacy or the safety assessments during study treatment administration.
- 10. Positive history of active liver disease (other than non-alcoholic hepatic steatosis), including chronic hepatitis B or C, primary biliary cirrhosis, or active symptomatic gallbladder disease.
- 11. Positive history of HIV.
- 12. Use of the following medications:
 - a. History of any basal, pre-mix or prandial insulin (greater than 7 days) within 6 months prior to Screening.
 - b. Administration of thyroid preparations or thyroxine (except in subjects on stable replacement therapy) within 6 weeks prior to Screening.
 - c. Administration of systemic long-acting corticosteroids within two months or prolonged use (more than one week) of other systemic corticosteroids or inhaled corticosteroids (if daily dosage is > 1,000 μg equivalent beclomethasone) within 30 days prior to Screening. Intra-articular and/or topical corticosteroids are not considered systemic.
 - d. Use of medications known to modify glucose metabolism or to decrease the ability to recover from hypoglycemia such as oral, parenteral, and inhaled steroids (as discussed above), and immunosuppressive or immunomodulating agents.
- 13. Known allergy to soy.
- 14. Subject is on a weight loss program and is not in the maintenance phase, or subject has started weight loss medication (e.g., orlistat or liraglutide), within 8 weeks prior to Screening.
- 15. Subject has had bariatric surgery.
- 16. Subject is pregnant or breast-feeding.
- 17. Subject is a user of recreational or illicit drugs or has had a recent history (within 1 year of Screening) of drug or alcohol abuse or dependence. (Note: Alcohol abuse includes heavy alcohol intake as defined by >3 drinks per day or >14 drinks per week, or binge drinking) at Screening. Occasional intermittent use of cannabinoid products will be allowed provided that no cannabinoid products have been used during the 1 week prior to each visit.
- 18. One or more contraindications to metformin as per local label.
- 19. History of gastrointestinal disorders (e.g. hypochlorhydria) with the potential to interfere with drug absorption.
- 20. At the Principal Investigator's discretion, any condition or other factor that is deemed unsuitable for subject enrollment into the study.

